12.5 Correlative studies (A221505-ST1)

We expect to enroll 880 patients to the treatment portion of this study. Assuming a 10% drop-out rate, we expect to have 792 patients evaluable for the primary endpoint. We further anticipate blood samples will be available for 80% of these patients, resulting in a total sample size of 634 patients for this biomarker sub-study. Assuming the 24-month breast reconstruction complication rate is 25%. The detectable differences were computed for various minor allele frequencies with 80% power using a one-sided type I error rate of 0.0036 ($= 0.05/14$, a Bonferroni correction for multiple

comparisons). The power calculations were based on a chi-square test of binomial proportions and assuming that the SNPs have recessive effect on 24-month breast reconstruction complication rate. The detectable differences are shown in Table 2 for a range of minor allele frequency for the SNPs shown in Table 1. Of particular interest, the allele frequency for MDM2 rs2279744 is close to 0.4. We expect approximately 101 out of 634 patients to be homozygous for this variant. There is sufficient power at this sample size and genotype frequency to detect an increase in 24-month complication rate from 25% (in the control group) to 42.5% (in the homozygous variant group) at the 1-sided type I error of 0.0036. The other scenarios in Table 2 represent the minimum (0.2) and the maximum (0.5) MAF for the SNPs represented in Table 1.

Table 2: Detectable Difference with 80% Power

Minor Allele Frequency	Number of patients		Detectable Difference (%)
	Homozygous variant	Non-homozygous variant	
0.2	25	609	33
0.4	101	533	17.5
0.5	158	476	15

Logistic regression model will be used to assess the association between each SNP and 24-month complication. The analysis will adjust for treatment arm and other baseline demographics and clinical factors as appropriate. We will also look at the frequencies separately by treatment arm as well as in both arms together (although we do not expect to see a difference in this non-inferiority study). Similar analysis will be conducted to evaluate the association between each SNP and lymphedema as well as local-regional recurrence.

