13.1 Correlative Science (Alliance A221505-ST1)

13.1.1 Background

The sequencing of the human genome has led to the discovery of several million single nucleotide polymorphisms (SNPs), some of which can alter gene function and account for unique traits between individuals. SNPs in certain genes associated with cellular function, such as cell cycle control, apoptosis, and DNA repair, can have significant functional consequences with respect to cancer susceptibility and cancer biology.^{88,89} Investigators at the Rutgers Cancer Institute of New Jersey have discovered a potentially important SNP at position 309 (SNP309, rs2279744; G→T) in the promoter region of *MDM2*.⁹⁰⁻⁹³ This *MDM2* proto-oncogene encodes a nuclear-localized E3 ubiquitin ligase. Heterozygous and homozygous polymorphisms in this location are relatively common, with homozygous mutations present in approximately 12% of normal volunteers. Experimental systems have demonstrated that cell lines homozygous for the polymorphism result in overexpression of the Mdm2 protein with subsequent attenuation of p53 activity.

The Mdm2 protein has been shown to be a key regulator of p53, and has been shown to inhibit p53 activity and promote its degradation.^{90,92,93} Overexpression of the Mdm2 protein resulting in lower levels of p53 results in high rates of tumor formation in animal models. Similarly, low levels of Mdm2 result in higher rates of apoptosis and increased sensitivity to radiation. Therefore, changes in the Mdm2 protein may affect both carcinogenesis and response to therapy, as a direct result of its regulation of the p53 pathway.^{90,92,93} As an example, Khor et al., recently analyzed expression of Mdm2 in a large cohort of men treated for prostate cancer on the RTOG 9202 study. On multivariate analysis in 487 patients, Mdm2 overexpression correlated with overall mortality and distant metastasis rate.⁹⁴ Similarly, Tu and colleagues sequenced both the *MDM2* rs2279744 and the p53 gene (TP53) SNP; at codon 72 (rs1042522; C→G; Pro72Arg) in 189 patients with oral cavity carcinoma treated with postoperative RT.⁸⁶ They found that patients carrying the G/G variant of *MDM2* rs2279744 or the Arg/Arg amino acid at codon 72 of TP53 had worse overall survival and disease-free survival than patients carrying other polymorphic variants. Interestingly, patients with both of the above variants in *MDM2* and TP53 had the highest hazard ratio for mortality and poor control.

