A PMRT study of two different fractionation schedules could be an ideal background for exploring possible associations of candidate SNPs with poor radiation outcomes such as Baker 3 or 4 contracture, reconstruction loss, and lymphedema. We hypothesize that a germline homozygous G/G variant of SNP309 in MDM2 will correlate with with a higher likelihood of adverse radiation reactions in a prospectively studied cohort of women receiving hypofractionated PMRT. Additional genes in the p53 and DNA repair axes as well as candidates in inflammatory pathways that have already been reported will be evaluated for validation (Table 1). Our work may identify groups of patients who are at risk for higher rates of radiation toxicity.

Table 1
List of 14 candidate SNPs from 10 genes

Number of SNPs	Genes	dbSNP id	Chromosome	Wild type (WT) allele	Variant allele	Global Frequency	
						Variant (minor) allele	Variant genotype (%)
1	FLT4	rs10464063	5	C	T	0.456	20.7
2	IL10	rs1518111	1	C	T	0.427	18.2
3	IL13	rs1800925	5	C	T	0.255	6.5
4	IL4	rs2070874	5	C	T	0.401	16.1
5	IL4	rs2227284	5	T	G	0.393	15.4
6	IL4	rs2243250	5	T	T	0.470	22.1
7	KDR	rs2239702	4	C	T	0.219	4.8
8	MDM2	rs1690924	12	T	C	0.346	12.0
9	MDM2	rs2279744	12	T	G	0.367	13.4
10	MDM2	rs937282	12	G	C	0.497	24.7
11	NFKB2	rs1056890	10	G	A	0.290	8.4
12	TGFB1	rs1800469	19	G	A	0.368	13.5
13	TP53	rs1042522	17	C	G	0.457	20.9
14	VEGFC	rs3775203	4	G	T	0.380	14.5

This phase III trial, in which all women will have post-mastectomy radiation therapy (PMRT) and an attempted chest wall reconstruction, has a primary endpoint of reconstruction complications at 24 months. We hypothesize that a polymorphism in MDM2 (position 309 (SNP309, rs2279744; T→G)) will correlate with a higher likelihood of having a reconstruction complication. The reconstruction complication endpoint is a composite endpoint as described in Section 2.1. Events that can trigger a scorable event for the primary endpoint are listed in Section 9.2 and include:

- Complete failure of the implant/skin flap.
- Unplanned re-operation(s),
- Re-operation for contracture management
- Unplanned admission for reconstruction related issue(s) including but not limited to infection, wound healing complication or pain

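### Section 12.5 credits the lead MDM2 SNP with 101 homozygous patients; the protocol's own frequency for it gives about 85, and power of about 73% rather than 80%

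*Combined protocol and SAP*

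**What the plan says.** Section 12.5 starts from 880 patients, allows 10% drop-out (792 evaluable) and assumes blood samples from 80% of these, "resulting in a total sample size of 634 patients for this biomarker sub-study". The power calculation uses a chi-square test of two proportions and a recessive model (homozygous variant against everyone else), "with 80% power using a one-sided type I error rate of 0.0036". That error rate is 0.05 divided by the 14 SNPs.

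Section 12.5 then singles out rs2279744, rounds its allele frequency to 0.4 and states "We expect approximately 101 out of 634 patients to be homozygous for this variant". It calls this enough to "detect an increase in 24-month complication rate from 25% (in the control group) to 42.5% (in the homozygous variant group"). The matching row of "Table 2: Detectable Difference with 80% Power" has 101 homozygous patients, 533 others and a difference of 17.5 points.

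Section 13.1.1 gives two other figures for the same SNP. Table 1 ("List of 14 candidate SNPs from 10 genes") has it in row 9 with minor allele frequency 0.367 and variant genotype 13.4%. The background text describes the polymorphism as common, "with homozygous mutations present in approximately 12% of normal volunteers". The same section makes rs2279744 the sub-study's primary hypothesis.

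**The concern.** The expected number of homozygotes depends on the square of the allele frequency, so rounding 0.367 up to 0.4 has more effect than it appears to: 13.4% becomes 16%, and 85 patients become 101, about 19% more. Under a recessive model the homozygotes are the small group, and their number largely determines the precision of the comparison.

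This is the only SNP with a power statement of its own. If the statement is too favourable, a null result for the primary hypothesis of the sub-study would be read against a power that the listed frequency does not give. At the stated effect, the chance of missing it would be about 27% rather than 20%.

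**Working it through.** **Inputs.** From Section 12.5: N = 634; p1 = 0.25 (non-homozygous); p2 = 0.425 (homozygous); one-sided alpha = 0.0036, so z = 2.687. From Section 13.1.1: allele frequency 0.367 and genotype 13.4% (Table 1), and about 12% homozygous (background text).

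**Expected homozygotes.**
- Section 12.5: 634 × 0.4² = 101.4, so 101 v 533.
- Table 1: 634 × 0.134 = 85.0 (634 × 0.367² = 85.4), so 85 v 549.
- Background text: 634 × 0.12 = 76.1, so 76 v 558.

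**Formula.** Two-proportion test with pooled variance under the null hypothesis and no continuity correction. With n1 non-homozygous and n2 homozygous patients, and p̄ = (n1·p1 + n2·p2)/634:
- SE0 = √[p̄(1 − p̄)(1/n1 + 1/n2)]
- SE1 = √[p1(1 − p1)/n1 + p2(1 − p2)/n2]
- Power = Φ[(p2 − p1 − z·SE0)/SE1]

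**Reproducing the plan.** With 101 v 533: p̄ = 0.2779, SE0 = 0.0486, SE1 = 0.0526. Power = Φ[(0.175 − 2.687 × 0.0486)/0.0526] = Φ(0.843) = 80.0%. Exact enumeration of the test gives 80.1%. Solving for the difference at 80% power gives 32.6, 17.5 and 14.8 points for 25, 101 and 158 homozygotes, against 33, 17.5 and 15 in Table 2. The alternatives tried give less than the stated 80% with 101 homozygotes: unpooled variance 73.8%, continuity correction 76.8%, arcsine 77.3%, two-sided 73.8%. The pooled one-sided test is therefore taken as the plan's method.

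**The same formula with the other two counts.**
- 85 v 549: p̄ = 0.2735, SE0 = 0.0520, SE1 = 0.0567, power = Φ(0.624) = 73.4% (exact enumeration 73.3%).
- 76 v 558: p̄ = 0.2710, SE0 = 0.0543, SE1 = 0.0596, power = Φ(0.486) = 68.6%.

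| Source of frequency | Homozygous v other | Power, 25% v 42.5% | Difference detectable with 80% power |
|---|---|---|---|
| Section 12.5, rounded to 0.4 | 101 v 533 | 80.0% | 17.5 points |
| Table 1, 13.4% | 85 v 549 | 73.4% | 18.8 points |
| Background text, about 12% | 76 v 558 | 68.6% | 19.7 points |

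**Reading of the 25%.** If 25% is taken as the overall rate and not the rate in non-homozygous patients, power is 82.6% with 101, 75.9% with 85 and 71.0% with 76. The loss from 101 to 85 is again about 7 points.

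**The case against.** The strongest reply is that this is an open approximation. Section 12.5 says that the frequency is near 0.4 and that the count is approximate. The multiplication is right, and each row of Table 2 is right for the frequency it states. The table is a grid over the SNPs in Table 1, and rs2279744 is matched to its nearest row. That stands as far as Table 2 goes. It does not cover the sentence that assigns 101 patients to this variant, because Table 1 prints the genotype frequency directly and no rounding was needed.

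A second reply is that Table 1 holds global frequencies. Section 13.1.3 warns of ethnic variation and asks for genotype data that match the trial's patients. The enrolment tables in Section 12.8 plan 516 + 274 = 790 White patients of 880, which is not a global mix. The true count could lie on either side: by the same formula, frequencies of 0.38, 0.39 and 0.41 give about 76%, 78% and 82% power. This stands as a limit on certainty. However, nothing in the documents supports 16% for this SNP, and both figures that they do give are lower.

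Third, the practical effect is modest. The detectable difference moves by 1.3 points, in a calculation that already rests on assumed rates of complications, drop-out and sample availability. The planned analysis is an adjusted logistic regression and not the chi-square test. The sub-study is optional for patients. All of that is true, and it limits the weight of the point.

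**Conclusion.** The point holds for the power stated for rs2279744. On the protocol's listed frequency for this SNP, about 85 homozygotes are expected and power for 25% v 42.5% is about 73%, with 18.8 points detectable at 80% power. On the 12% figure, power is about 69% and 19.7 points are detectable. This rests on the plan's recessive model, 634 samples, 25% in the non-homozygous group, one-sided 0.0036, and the pooled test inferred from Table 2.

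A reader might infer more, and the documents do not support it:
- **That 73% is the power the sub-study will have.** It is conditional on a global frequency; the documents give none for the trial's population.
- **That 12% is a floor.** It is another point estimate, from volunteers whose number and ancestry are not given.
- **That Table 2 is wrong.** Its 0.4 row is correct for 0.4 and fits two other SNPs in Table 1 closely: IL4 rs2070874 (0.401) and IL4 rs2227284 (0.393).
- **That the main trial is affected.** Its primary endpoint, sample size and error rates do not depend on this count.

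**What to change.** - In Section 12.5, replace 101 by about 85 for rs2279744. State either about 73% power for 25% v 42.5%, or a detectable difference of 18.8 points at 80% power, and say that this is conditional on the global frequency in Table 1.
- Show the 12% figure (76 patients, about 69% power, 19.7 points) as a sensitivity case, and reconcile it with the 13.4% in Table 1.
- Keep the 0.4 row of Table 2 as a generic scenario and add a 0.367 row for this SNP: 85 homozygous, 549 others, 18.8 points.

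The cost is wording in Section 12.5, one added row in Table 2, and a line to reconcile the frequencies in Section 13.1.1. Enrolment, sampling and analysis do not change. The stated power for the lead SNP becomes somewhat less favourable.

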12.6 Missing Data

If the proportion of missing patient information is larger than 5%, we will examine the missingness mechanism by modeling indicators of missing values as a function of baseline patient characteristics, observed patient-reported outcomes and missingness of patient-reported outcomes.

12.6.1 If as a result of this analysis, we feel it is reasonable to assume that missingness depends solely on the covariates (missing completely at random, MCAR) or depends on the covariates and observed PRO scores only (missing at random, MAR), we will enhance the primary analysis to incorporate these covariates. [85]

12.6.2 If as a result of this analysis, we feel the missingness likely depends not only on the covariates and observed PRO scores, but also on the missing PRO score (missing not at random, MNAR), we will explore advanced models.

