1.4 Patient Satisfaction and Well-being as Patient Reported Outcomes (PROs)

The assessment of patient-reported outcomes (PROs) in clinical research provides important insight into how therapies impact the daily lives of patients. There is a growing recognition that patient-reported endpoints are critical in oncology trials, particularly when cosmesis and toxicity are likely to be different in the treatment arms. Patient-reported adverse event collection has been shown to be more thorough than collection by provider-report, with consistent underreporting of side effects by providers.[69] Patient-reporting of health-related quality of life has become the gold standard in part because providers have been found to underestimate the pain and distress their patients are experiencing. [70-72]

In a trial of different radiation schedules, in which cosmesis may be substantially different in the two arms of the study, patient-reported satisfaction and well-being are particularly important. Although short-term differences between the treatment arms may be momentarily relevant to patients, the long-term cosmetic outcomes are most critical, so we have chosen to collect these data at 24 months (and compare to pre-treatment measures). In order to avoid burdening patients, we will not survey them for satisfaction or well-being in between these time points.

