12.4.4 Patient Reported Outcomes (PRO) Objectives

Physical well-being, psychosocial well-being, sexual well-being, satisfaction with breast/nipples/abdomen, and satisfaction with overall outcome between the treatment arms at 24 months after radiation: Change in LBCQ and BLE scores at 24 months post-radiation (relative to pre-RT) and patient satisfaction scores as measured by the Breast Q overall outcome scale will be summarized and will be compared across the treatment arms using a two-sample t-test with a two-sided alternative. Linear mixed models will also be used to assess these scores longitudinally.

Patient satisfaction with trial participation by treatment arm as measured by the Was It Worth It Questionnaire at 24 months after radiation: Was It Worth It questionnaire responses to each of the five questions at 24 months will be summarized and will be compared across treatment arms using a Chi-square tests with a two-sided alternative. In particular, for questions 1-3, the proportion of patients who answered “yes” will be compared across the two treatment arms, and for questions 4 and 5, we will compare the proportion of patients who answered “it got worse” and “worse than I expected” (respectively) across the two arms.

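### Section 12.6 chooses between MAR and MNAR analyses of the patient-reported outcomes with a model of observed data only, which cannot tell them apart, so a needed MNAR analysis may not be run

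*Combined protocol and SAP*

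**What the plan says.** Section 12.6 starts with a trigger: "If the proportion of missing patient information is larger than 5" per cent, the mechanism will be examined by "modeling indicators of missing values as a function of baseline patient characteristics, observed patient-reported outcomes and missingness of patient-reported outcomes". Two branches follow, each chosen on the result of that model.

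- **12.6.1.** If missingness is thought to depend only on covariates (which the plan calls MCAR), or on covariates and observed PRO scores (MAR), then "we will enhance the primary analysis to incorporate these covariates".
- **12.6.2.** The condition begins "If as a result of this analysis, we feel the missingness likely depends not only on the covariates and observed PRO scores". The rest of the sentence brings in the unobserved score and states the action: "but also on the missing PRO score (missing not at random, MNAR), we will explore advanced models". No criterion is given and no model is named.

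Section 12.4.4 gives the main PRO analyses. Changes in LBCQ and BLE scores and the Breast-Q outcome score are "compared across the treatment arms using a two-sample t-test with a two-sided alternative". It adds: "Linear mixed models will also be used to assess these scores longitudinally". For satisfaction and well-being, Section 1.4 says of the interval between pre-treatment and 24 months that "we will not survey them for satisfaction or well-being in between these time points".

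The sensitivity analyses named elsewhere concern stratification by reconstruction (Section 12.3.2) and imputed cost parameters (Section 12.4.5). Neither deals with missing PRO data.

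**The concern.** The two branches differ in one thing only: whether missingness depends on the score that was not observed. That score cannot be a regressor in the model meant to decide the matter. A link between missingness and observed scores, which 12.6.1 takes as a sign of MAR, also appears under MNAR whenever observed and unobserved scores are correlated.

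This trial gives reasons to take the possibility seriously. It is un-blinded (Section 12.1), and Breast-Q booklets may be returned by mail (Section 10.4.1). Required follow-up ends after recurrence, a second cancer or alternative treatment (Section 11.3.2). Section 1.6 hypothesises better cosmesis, lymphedema and quality of life with hypofractionation. If dissatisfied women in Arm 2 return fewer 24-month booklets, the observed comparison tilts towards that hypothesis. The plan could then report an analysis valid only under MAR, having decided from uninformative evidence that nothing further was needed.

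**Working it through.** **1. Logic.** Let R indicate that the 24-month score Y is missing, and let X be everything observed (baseline data, other PROs and their missingness).

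- What 12.6 can fit: P(R = 1 | X).
- What separates the branches: whether P(R = 1 | X, Y) varies with Y.

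Y is absent exactly where R = 1, so the second quantity cannot be estimated without untestable assumptions. Any fitted P(R = 1 | X) is compatible with both branches.

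**2. Inputs.** Section 12.6 contains no figure except the 5% trigger. The group size is 396 per arm (Section 12.2). It reproduces: (1.960 + 1.282)² × 2 × 0.25 × 0.75 / 0.10² ≈ 394.1, rounded up to 395, against 396 stated. The documents give no PRO SD, missing rate, baseline to 24-month correlation or PRO alpha. Assumed: SD 1, correlation 0.5, two-sided 0.05 and no true arm difference.

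**3. Can the diagnostic discriminate?** Trials were simulated with a logistic model of missingness on arm and baseline score, then a baseline-adjusted comparison of complete cases (1,500 trials per mechanism).

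| Assumed truth | Missing, Arm 1 / Arm 2 | Baseline predicts missingness | Arm predicts missingness | Bias (SD) | False positives |
|---|---|---|---|---|---|
| MAR: logit = -1.6 + 0.4·arm - 0.5·baseline | 18% / 24% | 99.9% of trials | 63% | 0.00 | 5.3% |
| As above, plus the unseen part of the 24-month score in Arm 2 (slope -1.0) | 18% / 27% | 99.9% of trials | 86% | 0.17 | 70% |

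In both rows the analyst sees missingness linked to baseline score and often to arm, and in a single trial that pattern does not show which row is true. This pair serves only to compare the diagnostic; its second mechanism is harsher than those used for size below.

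**4. Size.** Now logit(missing) = intercept - slope × 24-month score, with the slope set by arm. The intercept is -1.5 for the rows with about 20% missing and lower for the rows with about 9%.

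| Slopes, Arm 2 vs Arm 1 | Missing | Bias (SD) | False positives |
|---|---|---|---|
| 1 vs 1 | 22% | 0.00 | 4.8% |
| 0.75 vs 0.5 | about 20% | 0.035 | about 7-8% |
| 0.5 vs 0 | about 20% | 0.065 | 16% |
| 1 vs 0.5 | about 20% | 0.075 | about 18-19% |
| 1 vs 0 | about 20% | 0.142-0.145 | about 55-58% |
| 1 vs 0.5 | about 9% | 0.038 | 9.5% |
| 1 vs 0 | about 9% | 0.071 | about 18-19% |

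Hand check at 20% missing: the residual variance is 1 - 0.5² = 0.75, so SE ≈ √(2 × 0.75 / (396 × 0.8)) = 0.069. The false-positive rate is 1 - Φ(1.96 - bias/SE) + Φ(-1.96 - bias/SE). Bias 0.035 gives 8%, 0.075 gives 19% and 0.143 gives 55%, in line with the simulation.

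**5. Size by missing rate.** Suppose non-respondents in one arm differ by δ SD, with missing fraction m. Then bias = δ × m and, unadjusted, SE = √(2 / (396(1 - m))). For δ = 0.5 and m = 0.20, bias is 0.10, SE is 0.0795 and the false-positive rate is 24.2%.

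| Missing | δ = 0.2 | δ = 0.5 | δ = 0.8 |
|---|---|---|---|
| 5% | 5.2% | 6.4% | 8.5% |
| 10% | 5.8% | 10.2% | 18.7% |
| 20% | 7.9% | 24.2% | 52.1% |
| 30% | 10.9% | 42.3% | 80.7% |

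**The case against.** The plan does contain an MNAR route, and its wording leaves room for clinical judgement, so the team could enter 12.6.2 whatever the model shows. A reader might infer that the plan has no MNAR provision at all; the text does not support that. What stands is narrower: the route is conditional, the stated basis for taking it cannot inform the choice, and the method is unnamed.

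A fuller diagnostic would also see more. In the case of slopes 1 vs 0, a model with arm and baseline main effects flags arm in only about 26-29% of trials; adding an arm-by-baseline term raises this to about 70-73%. EQ-5D at 6, 12 and 18 months and LBCQ at 6 months are available as further predictors. This is fair, and such a flag could prompt discussion. It still would not identify MNAR, since MAR can produce arm-related missingness too.

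A reader might also pair near-certain detection of baseline dependence with the highest false-positive rate. Those belong to different cases. When MNAR acts equally in both arms (slopes 1 vs 1), baseline dependence appears in 99.9% of trials and the comparison is unbiased. In the harmful case (1 vs 0) it appears in about 70%.

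The planned mixed models already provide a MAR analysis. That is true, but they protect under MAR only, and Breast-Q has no intermediate scores to support the assumption.

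**Conclusion.** The point holds for the secondary PRO comparisons. Section 12.6 makes an MNAR analysis depend on a model that cannot show whether one is needed, and no other section prespecifies one.

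Under the stated assumptions the consequence ranges from none (MNAR equal in both arms) to a bias of about 0.15 SD with 55-58% false positives (slopes 1 vs 0, about 20% missing). Milder arm-specific cases give about 7% to 19%. Harm is small near the 5% trigger, so the absence of any action at or below it matters little. The documents offer no evidence that non-response will differ by arm: bias is possible, not shown.

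Because 12.6.1 speaks of the primary analysis, a reader might infer that the complication endpoint is at risk. The conditions in 12.6.1 and 12.6.2 are framed in terms of PRO scores, so the primary endpoint, its margin and the sample size are not touched by this point. A change is advisable, but it is not critical to the trial's main conclusion.

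**What to change.** Replace the choice between 12.6.1 and 12.6.2 with the following.

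- State MAR as the working assumption for the main PRO analysis, and keep the missingness model as a description only.
- Whenever more than 5% of a 24-month PRO is missing, always report a prespecified arm-specific MNAR sensitivity analysis.
- For continuous scores, use delta-adjusted multiple imputation with a tipping point. Shift in the worse direction for each instrument: down for Breast-Q, up for LBCQ and BLE, where higher means more symptoms. Make the range wide enough to reach the tipping point.
- Condition on the baseline score only where a comparable one exists. Women not yet reconstructed complete a different Breast-Q module before radiation and no baseline BLE (Section 5.0).
- For the Was It Worth It items, which are categorical and collected only at 24 months, vary the assumed response proportions among non-responders by arm.
- In 12.6.1, relabel MCAR as covariate-dependent missingness, and say which analysis is meant by the primary one.

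Cost: SAP wording and one standard analysis per PRO, with no new data, visits or patients. It takes a little more programming, and some PRO conclusions may prove fragile.
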